10.2.4 Secondary Analysis

1. For the secondary objective we will compare the efficacy of bupivacaine with that of lidocaine over the postoperative 5 days using mixed models for longitudinal data. The efficacy will be compared in terms of the following measures: postoperative pain resolution,
2. pain medication use,
3. numbness (duration of LA) after receiving endodontic treatment

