The null hypothesis of this study is that there is no difference between a group of subjects exposed to Bupivacaine, a LLA vs. a group exposed to Lidocaine for dental anesthesia regarding oral quality of life change in subjects with preoperative pain (at least 3/10 on Numerical Rating Scale (NRS)) and diagnosed with a pulpal diagnosis of either symptomatic irreversible pulpitis or pulp necrosis and periapical diagnosis of normal periapical tissues, asymptomatic or symptomatic apical periodontitis who will receive pulpectomy/endodontic debridement on a mandibular molar.

It is well established that one of the major predictors of postoperative pain is the preoperative pain associated with the offending tooth. (2). This fact is the rational why only subjects with symptomatic teeth (with preoperative pain at least 3/10) will be recruited from endodontic services on NRS. Bupivacaine or Lidocaine (chosen randomly) will be administered double blinded prior to the endodontic procedure to

CONFIDENTIAL

anesthetize the pulp and surrounding bone with inferior alveolar nerve block (IANB) in lower molars with a dosage of one cartridge. This is a routine route of administration and dosage applied in routine endodontic practice. If the IANB fails, a second cartridge will be administered, again routinely recommended and done in clinical practice.

Some controversy exists in the literature regarding the success of bupivacaine for pulpal anesthesia during the treatment (15-18) because of methodological differences and different inclusion criteria. Also, delayed onset time may be a disadvantage of bupivacaine although, the onset time has been found comparable to lidocaine and there was no statistically significant difference, in mandibular molar teeth (16). However, because of these controversies in literature, success and onset of LA will be also captured and recorded and analyzed in the study without no additional interventions

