3.2 Secondary Objectives

1. Compare the pulpectomy/endodontic debridement treatment of 0.5% bupivacaine with 1:200,000 epinephrine, as a LLA, with pulpectomy/endodontic debridement treatment of with 2% Lidocaine with 1:100,000 epinephrine, as a LLA, with respect to changes in postoperative pain over days 1-5.
2. Compare the pulpectomy/endodontic debridement treatment of 0.5% bupivacaine with 1:200,000 epinephrine, as a LLA, with pulpectomy/endodontic debridement treatment of with 2% Lidocaine with 1:100,000 epinephrine, as a LLA, with respect to duration of pain medication use over days 1-5
3. Compare the pulpectomy/endodontic debridement treatment of 0.5% bupivacaine with 1:200,000 epinephrine, as a LLA, with pulpectomy/endodontic debridement treatment of with 2% Lidocaine with 1:100,000 epinephrine, as a LLA, with respect to duration of anesthesia (numbness) after treatment.

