5.1 Inclusion Criteria

In order to be eligible to participate in this study, an individual must meet all of the following criteria:

1. Patients between the ages of 18-85 years old.
2. Patients with pulpal diagnosis of either symptomatic irreversible pulpitis or pulp necrosis and periapical diagnosis of normal apical tissues, symptomatic apical periodontitis or asymptomatic apical periodontitis.
3. Patients who only have one tooth with odontogenic pain at the time point of the screening.
4. Patients who are treatment planned, and have agreed to have, pulpectomy/endodontic debridement.
5. Patients with acute dental pain of at least 3/10 on NRS.
6. Patients must be able to comprehend and complete all study questionnaires.
7. Patients must be able to comprehend the description of the study protocol and written consent.
8. Patients must be available to be contacted by text messages, phone calls or email during 5 days after the pulpectomy/endodontic debridement.

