10.2.2 Descriptive Statistics

Within each randomized treatment group appropriate descriptive statistics including means and standard deviations for quantitative variables and frequency and percentages for categorical variables will be calculated. Wilcoxon Rank Sum test and Fisher's exact test will be used to compare the two intervention groups with respect to the following baseline variables:

- Demographics (age, sex, race, ethnicity)
- Initial pain intensity and duration
- Pain medication use
- Pain Catastrophizing Scale
- Initial diagnosis (symptomatic irreversible pulpitis with/without symptomatic apical periodontitis and pulp necrosis with symptomatic apical periodontitis)
- Initial clinical testing of cold response (positive/negative)
- Initial clinical testing of percussion hypersensitivity (painful/not painful)

Any variable deemed significant will be controlled for in the primary, secondary and exploratory analyses. All analyses will be done with significance level of 5% (2-sided) unless specified otherwise.

CONFIDENTIAL

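### Preoperative pain enters the postoperative pain model only if a baseline significance test flags it, so the first secondary comparison will usually lose precision that prespecified adjustment would give at almost no cost

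*Combined protocol and SAP*

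**What the plan says.** Secondary objective 1 (section 3.2) compares the arms "with respect to changes in postoperative pain over days 1-5". The matching endpoint in section 4.1.2 is pain intensity over the five postoperative days. Pain is scored on an NRS at 6, 12, 24, 48, 72, 96 and 120 hours (sections 7.1.1 and 7.2.3).

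Section 10.2.4 describes the analysis in one clause: "we will compare the efficacy of bupivacaine with that of lidocaine over the postoperative 5 days using mixed models for longitudinal data". It lists no fixed effects, no covariates and no handling of the preoperative score.

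Section 10.2.2 supplies a general covariate rule. "Wilcoxon Rank Sum test and Fisher's exact test will be used to compare the two intervention groups" on a list of baseline variables that includes "Initial pain intensity and duration". It continues: "Any variable deemed significant will be controlled for in the primary, secondary and exploratory analyses". The level is given next: "All analyses will be done with significance level of 5% (2-sided) unless specified otherwise".

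On preoperative pain itself, section 2.3 states: "It is well established that one of the major predictors of postoperative pain is the preoperative pain associated with the offending tooth". Eligibility depends on it (section 5.1: "Patients with acute dental pain of at least 3/10 on NRS"). Section 7.1.1 collects it before treatment, and section 10.2.1 includes it in the analysis dataset.

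**The concern.** A covariate earns its place in a randomized comparison by predicting the outcome. A significant baseline difference between arms is not the criterion, because after randomization such a difference is a chance event. The plan uses that criterion. It has a variable on the same kind of scale as the outcome, collected before treatment and described as strongly prognostic, yet lets it into the pain model only when chance has separated the arms on it.

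At stake is the width of the interval for the arm difference in pain and the power of that comparison. In addition, the form of the model will be known only after the baseline data have been tested.

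**Working it through.** **1. The plan's own figure.** The only power statement is for the OHIP-14 primary outcome (section 10.1): 40 per arm, difference 9.3, SD 13.3, two-sided 2.5%, 80% power. The standardized difference is 9.3/13.3 = 0.699. A two-sample t-test then has 79.8% power, the difference detectable with 80% power is 9.32, and 40/(1 − 0.2) = 50 per arm gives 100 in total. The figure reproduces, and it does not depend on this point. The documents state no power, SD or correlation for pain.

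**2. How often the 10.2.2 rule admits preoperative NRS.** The baseline test is run at 5%. Under 1:1 randomization the null hypothesis for a baseline variable is true, so the test is significant in about 5% of trials. Simulation (step 5) gave 4.9% to 5.2%. In about 95% of trials the pain model would therefore omit the variable.

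**3. Variance.** Let r be the correlation between preoperative NRS and the postoperative NRS averaged over follow-up. Compared with a model without baseline, the variance of the adjusted arm difference is multiplied by 1 − r², and the interval width by √(1 − r²). The values of r are assumptions.

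**4. Power if always adjusted.** With 40 per arm and a two-sided 5% test, an effect of 0.634 SD has 80% power unadjusted. After adjustment the effective standardized difference is 0.634/√(1 − r²). At r = 0.3 this is 0.634/0.954 = 0.665. At r = 0.5 it is 0.634/0.866 = 0.732.

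| Assumed r | Variance cut (r²) | Interval narrower by | Power, always adjusted |
|---|---|---|---|
| 0.1 | 1% | 0.5% | 80.4% |
| 0.2 | 4% | 2.0% | 81.6% |
| 0.3 | 9% | 4.6% | 83.6% |
| 0.4 | 16% | 8.3% | 86.4% |
| 0.5 | 25% | 13.4% | 89.9% |
| 0.6 | 36% | 20.0% | 93.8% |

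**5. Power under the plan's rule.** This was simulated with 10,000 trials per setting, 40 per arm, normal baseline and averaged outcome, and adjustment only if the baseline Wilcoxon p-value was below 0.05.

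| Assumed r | Never adjusted | Plan's rule | Always adjusted | Type I error, plan's rule |
|---|---|---|---|---|
| 0.3 | 80.2% | 80.4% | 83.5% | 4.7% |
| 0.5 | 80.1% | 81.1% | 89.9% | 4.3% |

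The rule recovers little of the available gain: (80.4 − 80.2)/(83.5 − 80.2) = 0.2/3.3, about 6%, at r = 0.3, and (81.1 − 80.1)/(89.9 − 80.1) = 1.0/9.8, about 10%, at r = 0.5. Type I error does not exceed 5%, so the cost is efficiency and not false positives.

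**The case against.** **Section 10.2.4 is silent, and silence is not omission.** The objective speaks of changes in pain and the analysis of its resolution. Either could mean that the preoperative score enters as a time-0 response or through change scores. This stands in part, and it affects the comparator. A time-0 response with a common baseline mean would already capture most of the gain. Change scores, with equal variances, have relative variance 2(1 − r): 1.40 at r = 0.3 and 1.00 at r = 0.5, against 0.91 and 0.75 with covariate adjustment. But no text adopts either approach, the endpoint is worded as postoperative intensity, and the only stated rule that brings in baseline pain is the one in 10.2.2.

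**The correlation may be low.** This stands. Entry at NRS 3 or more narrows the baseline range. Rescue analgesics are allowed (section 7.6), and bupivacaine anesthesia may outlast the 6-hour assessment. Calling a variable a major predictor does not supply a correlation.

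**It is a secondary outcome without a power target.** This also stands, and it limits the weight of the point.

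Three stronger readings are tempting. A reader might infer that the model can contain no preoperative NRS term at all; 10.2.2 contradicts this, since its rule expressly reaches the secondary analyses. A reader might infer that a chance baseline difference too small to be flagged adds a separate bias; under randomization it is part of the same sampling variance already counted above. A reader might quote the upper end, 1/(1 − 0.36) = 1.56, as 56% more patients for free; that needs r = 0.6, which nothing in the documents establishes.

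**Conclusion.** The point holds as a loss of efficiency. Unconditional adjustment for preoperative NRS is not prespecified, and the conditional rule would supply it in about one trial in twenty. If r is 0.3, the plan gives up about 3 power points (80.4% against 83.5%); if r is 0.5, about 9 (81.1% against 89.9%). At r of 0.2 or below the loss is under 2 points and hardly matters.

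These sizes rest on an assumed correlation, 40 analysed per arm, an effect that has 80% power without adjustment, approximate normality, and a comparator without baseline. Neither the validity of the pain comparison nor the primary OHIP-14 conclusion is threatened. The change is worth making because it costs almost nothing and fixes the model before the data are seen.

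**What to change.** In section 10.2.4, state that the NRS scores at the seven postoperative times will be analysed with a mixed model containing arm, time, arm-by-time and preoperative NRS as a fixed covariate, whatever the baseline comparison shows.

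In section 10.2.2, remove the significance-triggered adjustment rule, or state that it does not govern this covariate. Changing 10.2.4 alone would leave two covariate rules for one model.

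The cost is one sentence in each section and one degree of freedom. No new data are needed, because the score is already collected.

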Statistical Analysis	
For the primary objective we will compare the oral quality of life OHIP-14 score change from preoperative baseline to day 1 postoperatively and the change from preoperative baseline to day 5 postoperatively between the 2 arms using a Wilcoxon Rank Sum test for each comparison individually at 2.5% significance level (2-sided) adjusted for the two comparisons using a Bonferroni correction. If at least one of the changes, either from baseline to day 1 postoperatively or from baseline to day 5 postoperatively, is significantly different between the 2 groups, the null hypothesis will be rejected.
 
For each of the 7 sub-domains of OHIP-14 we will calculate the mean change from preoperative baseline to day 1 and to day 5 in both arms.
 
For the secondary objective we will compare the efficacy of bupivacaine with that of lidocaine over the postoperative 5 days using mixed models for longitudinal data. The efficacy will be compared in terms of the following measures:
 
1. postoperative pain resolution2. pain medication use3. numbness (duration of LA) after receiving endodontic treatment 
The success of LLA will be determined by the cold test results (+/-) and the number of supplemental injections. The onset of LLA will be determined by the duration until adequate lip numbness and the duration until negative cold response after IANB.
 
For the exploratory objective we will compare the success and onset of LA in the two study arms. For comparison of success of LLA between the 2 arms we will use Fisher's exact test. For comparison of onset of LLA between the 2 arms we will use a Wilcoxon Rank Sum test.
 
Ad Hoc Stopping Rule
 
After 40 patients are accrued (approximately 20 subjects in each arm) an ad-hoc analysis will be performed to assess and compare the success of LA in both groups. If the proportion of subjects who are excluded intraoperatively in the study arm is twice as large as that of the control arm, the study will be terminated. The reasons for being excluded intraoperatively are if adequate lip numbness is not obtained with 2 inferior alveolar nerve block anesthesia and/or adequate pulpal anesthesia is not obtained after 2 times of supplemental anesthesia. Although, this is not a safety issue, we do not want to create more risks of intraoperative pain than routine endodontic practice. This analysis will be done by the study statistician. The investigators will remain blinded to the subjects' treatment arm.

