2.1 Background Information and Relevant Literature

Patients have been reported to suffer from moderate to severe pain after endodontic treatment for up to seven days, and of those the first 2 days pain is commonly the most severe (1). It has been shown that preoperative pain is the one of the major predictors of postoperative pain (2) which suggests that postoperative pain management becomes even more crucial for patients who report to the clinic with ongoing preoperative pain.

It has also been found that preoperative percussion hypersensitivity (mechanical allodynia) of an offending tooth has been shown to be one of the major predictors of severe postoperative pain after emergency treatments (3), 92% of the patients who attended emergency endodontic clinic had a painful response to percussion on the tooth in questions (4). Percussion hypersensitivity has been associated with central sensitization (5, 6) therefore, postoperative pain management can be an especially important in patients with a diagnosis of symptomatic apical periodontitis and painful percussion responses.

Postoperative management strategies have been suggested that usually include non-steroid anti-inflammatory drugs (NSAID) and/or acetaminophen (7), opioids (8), and corticosteroids (9). Alternatively, administration of LLA, bupivacaine, which can last up to 7-12 hours, has been suggested as a strategy to manage postoperative pain (10-12). A meta-analysis on efficacy and safety of bupivacaine versus lidocaine showed statistically significant better postoperative pain control with bupivacaine after dental treatment and no difference in safety when compared with lidocaine (10). It has been hypothesized that with the use of LLA, inhibits peripheral barrage from primary afferent neurons after the treatment and thereby significantly inhibit sensitization of second order neurons in the pain pathway that then will lead to reduction or elimination of central sensitization resulting in reduction of postoperative pain, not only during the LLA period but also after the resolution of the anesthesia (13).

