2.4.2 Known Potential Benefits

There may be no direct benefits to subjects for participating in this research study.

Bupivacaine HCl lasts two to three times longer than lidocaine, in many patients up to 7 hours. This may be beneficial if the treatment duration is longer and it may also help managing postoperative pain (11) that might reduce the analgesic use.

The post-treatment pain monitoring involved in this study may help us to identify subjects needing additional or quicker follow up with their clinical provider than would routinely occur.

3 Objectives and Purpose

This is a double-blind randomized controlled single-site trial. The purpose of this trial is to compare oral health related quality of life change, postoperative pain resolution, and to evaluate pain medication use and duration of anesthesia in subjects with preoperative pain (at least 3/10 on NRS) and diagnosed with a pulpal diagnosis of either symptomatic irreversible pulpitis or pulp necrosis and periapical diagnosis of normal periapical tissues, asymptomatic or symptomatic apical periodontitis who either receive LLA (0.5% bupivacaine with 1:200,000 epinephrine) or LA used as standard of care (2% lidocaine with 1:100,000 epinephrine) for pulpectomy/endodontic debridement at NYU Dentistry Endodontic Clinic.

Bupivacaine is a FDA approved anesthesia, which provides anesthesia up to 7 hours following administration. It is approved for use in dentistry both for infiltration and block anesthesia. We will evaluate

CONFIDENTIAL

This material is the property of the NYU School of Medicine and Langone Medical Center. Do not disclose or use except as authorized in writing by the study sponsor

oral quality of life change in subjects as well as the reported pain resolution and duration of postoperative pain in subjects who will undergo pulpectomy/endodontic debridement for a mandibular molar.

Controversies in literature regarding the success and onset of LA exist. This is why an exploratory objective will capture, record and analyze the success and onset of LA in two study arms in the study without additional interventions.

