4.1.2 Secondary Study Endpoints

- Postoperative pain intensity during 5 days
- Number and type of pain medication use
- Duration of LA in hours (numbness) after receiving pulpectomy/endodontic debridement

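### The first secondary outcome is pain intensity in the endpoint list, change in pain in the objective and undefined pain resolution in the analysis, and the mixed model does not say which contrast is tested

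*Combined protocol and SAP*

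**What the plan says.** The first secondary outcome has a different name at each level of the plan.

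- **Endpoint** (section 4.1.2 and the Protocol Summary): "Postoperative pain intensity during 5 days".
- **Objective** (section 3.2 and the Protocol Summary): a comparison "with respect to changes in postoperative pain over days 1-5". No reference point for the change is given.
- **Analysis** (section 10.2.4 and the Protocol Summary): "The efficacy will be compared in terms of the following measures: postoperative pain resolution". The method is a comparison "over the postoperative 5 days using mixed models for longitudinal data".
- **Purpose** (section 3, Objectives and Purpose): the trial will evaluate quality of life "as well as the reported pain resolution and duration of postoperative pain in subjects".

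Pain is collected on an NRS at 6, 12, 24, 48, 72, 96 and 120 hours (sections 7.1.1 and 7.2.3). Preoperative pain is also recorded (sections 7.1.1 and 10.2.1). The plan gives no NRS threshold for resolution, no rule on whether it must be sustained, no rule for analgesic use and no censoring rule. Section 2.1 says: "Patients have been reported to suffer from moderate to severe pain after endodontic treatment for up to seven days".

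**The concern.** Level, change and resolution are different variables. They need not agree in size or even in sign. A mixed model on repeated NRS scores can test a treatment main effect (level) or an arm-by-time term (change), and section 10.2.4 names neither. The words days 1-5 also leave open whether the 6 h and 12 h surveys count. Those are the surveys nearest the period of up to 7 hours in which section 2.2.1 says bupivacaine anesthesia may last.

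Two things are at stake. The analysed variable may not be the listed endpoint. And if the objective is followed literally as a change within days 1-5, an early benefit can be reported as a disadvantage. With no contrast named, the choice could also be made after the data are seen.

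**Working it through.** **What the plan computes.** It gives no power or effect figure for pain, so there is none to reproduce. The 40 per arm used below comes from section 10.1. The primary calculation there is sound (difference 9.3, SD 13.3, two-sided 2.5%: exact t power 79.8%) and this point does not touch it.

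**Inputs.** From the documents: seven surveys at 6 to 120 h, 40 per arm, two-sided 5% (section 10.2.2). Assumed, because the documents give no values: between-patient SD 1.8, residual SD 1.3, and a bupivacaine benefit that fades across the seven surveys as 2.5, 2, 1.2, 0.6, 0.3, 0.1, 0 NRS points. The 24 to 120 h surveys are taken as days 1 to 5.

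**Step 1: level.**
- Mean benefit = (2.5 + 2 + 1.2 + 0.6 + 0.3 + 0.1 + 0)/7 = 6.7/7 = 0.96 points, favouring bupivacaine.
- SD of a patient mean = √(1.8² + 1.3²/7) = 1.87. SE = 1.87 × √(2/40) = 0.417.
- z = 0.957/0.417 = 2.29, so power ≈ Φ(2.29 − 1.96) = 63%.

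**Step 2: slope over days 1-5.** The benefits are 1.2, 0.6, 0.3, 0.1, 0.
- Slope of the benefit = Σ(day − 3) × benefit / 10 = (−2.4 − 0.6 + 0 + 0.1 + 0)/10 = −0.29 points per day. Bupivacaine pain therefore falls 0.29 points per day more slowly, which favours lidocaine.
- With a random-slope SD of r points per day, SD of a patient slope = √(1.3²/10 + r²) and SE = SD × √(2/40).

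| r (assumed) | SE | z | Power, normal formula | Simulated, significant for lidocaine |
|---|---|---|---|---|
| 0 | 0.092 | 3.15 | 88% | 86% |
| 0.3 | 0.114 | 2.55 | 72% | 73% |
| 0.5 | 0.145 | 2.00 | 52% | 56% |
| 0.8 | 0.201 | 1.44 | 30% | 35% |

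The simulations use the same SDs and benefits, with an assumed control decay from about 5 and scores rounded and floored at 0, so they differ somewhat from the formula. With r = 0, mean intensity was 1.87 against 2.72 in favour of bupivacaine, with about 69% to 70% power. The slopes were −0.27 and −0.53 points per day.

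**Step 3: change from preoperative baseline.** Randomised arms share the same expected baseline, so the expected difference in change equals the difference in level.
- All seven surveys: 0.96 points favouring bupivacaine by the inputs. Simulated: 0.88 points, significant in 84%.
- 24 to 120 h only: 2.2/5 = 0.44 points, still favouring bupivacaine. Simulated: 0.39 points, significant in 24%.

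The sign does not reverse on this reading.

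**Step 4: resolution.** A patient still in pain at 120 h is unresolved on a yes/no definition and right-censored on a time-to-event definition. The exact time to resolution is not observed. Section 2.1 expects that some patients have pain beyond 120 h (five days), and a mixed model is not a time-to-event method.

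**The case against.** The strongest defence is that the documents already point one way. One pain variable is collected (NRS at fixed times), one pain endpoint is listed (intensity), and one method is named (mixed models for longitudinal data). Repeated NRS scores fit all three, with resolution as loose wording for pain that falls over time. No log-rank or responder analysis appears anywhere. Where the plan does define a change, for OHIP-14, it is from preoperative baseline, and on that reading nothing reverses.

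Most of this stands, and it narrows the choice. It does not close it. A level contrast and an arm-by-time contrast both fit the same model, and those are the two that can take opposite signs. Unlike the primary objective in section 3.1, the pain objective in section 3.2 names no preoperative baseline.

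Three stronger readings are tempting and are not supported.
- A reader might infer that resolution cannot be scored for patients still in pain at 120 h. It can, as shown in step 4.
- A reader might infer that the objective necessarily reads an early benefit as harm. It does so only under the slope reading.
- A reader might infer an inflated false-positive rate from three candidate outcomes. Simulating no effect and testing intensity, slope and sustained resolution together gave at least one significant result in 11.9% of runs. But the plan states one pain analysis, not three tests, so that figure does not describe it.

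**Conclusion.** The inconsistency is real and is in the text: one secondary outcome has three labels, resolution has no definition, and the model contrast is not named. The possible reversal of sign is conditional. It needs an early benefit that fades and a slope over 24 to 120 h as the contrast. Under those conditions the slope was significant for lidocaine in about 35% to 86% of simulated runs, with the upper end assuming that recovery rate does not vary between patients. The decay, SDs and benefit profile are all assumed, so these figures show the mechanism and are not forecasts. The primary endpoint, its significance level and the sample size are untouched. The point should be corrected, because the outcome bears directly on the pain-control rationale in section 2.3.

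**What to change.** In section 3.2, section 10.2.4 and the Protocol Summary, replace both the change wording and the resolution wording with NRS pain intensity as listed in section 4.1.2. In section 10.2.4, specify a mixed model on the repeated scores at all seven surveys (6 to 120 h), with preoperative NRS as a covariate, and name the between-arm difference in level averaged over the surveys as the estimate. Bring the purpose statement in section 3 into line.

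If resolution or duration is kept, label it supportive and define it. One option is the first survey from which NRS stays at 0, with patients still in pain at 120 h counted as unresolved and censored there, compared by a log-rank test. State how analgesic use is handled in that definition.

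The cost is wording, made before unblinding, with no new data or patients. The small downside is that resolution and duration become supportive results.
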